Capsaicin will be applied directly to the region of the innervation zone at the muscle belly to sensitize the neurons within the region of taut band development. Topical and intramuscular capsaicin will be used. The capsaicin formula will be compounded by a registered pharmacist. Topical capsaicin will be delivered in a cream and injectable capsaicin will be intermixed with saline prior to injection. The control group in the topical capsaicin arm will be treated with the cream base used during the experiment without added capsaicin and the injection arm will be injected with saline. A trained medical professional on the research team will apply the topical capsaicin or topical placebo treatments. The region of topical application will measure 5cm squared in the dermatome zone location to cover an area of approximately 25cm². A trained physician in physical medicine and rehabilitation will deliver injectable capsaicin using a 27-gauge needle at the location of the superior fascia of the upper trapezius muscle with ultrasound guidance. The fascial layer was chosen as it is the region with the lowest pressure pain threshold relative to skin and muscle, suggesting a high density of nociceptors within the layer, and it possesses connections to the spinal cord.[27] Changes in muscle fascia properties and nociception at muscle fascia, compared to nociception at muscle or subcutaneous tissue, has also been implicated in the development of pain.[28,29] Furthermore, intramuscular capsaicin will also be injected using ultrasound guidance to avoid the superior or inferior fascia.

To confirm the presence of central sensitization, brush allodynia will be used to detect mechanical hyperalgesia outside the region of primary nociception—region of topical placement or injection—which is the region of secondary hyperalgesia.[13-15] The size of the region of secondary hyperalgesia will be measured to characterize the extent of central sensitization. This will be accomplished using a tape measure and the perpendicular dimensions of the region of secondary hyperalgesia will be recorded in square centimeters.

Ultrasound analysis

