The Delsys Trigno system, which includes sensors, the Trigno base station, and the EMGworks software will be used to decompose the acquired EMG signals into individual motor units. The following parameters will be analyzed: the firing times and frequency of individual motor units, motor unit action potential amplitude and shapes[36-38], the root mean square value (RMS) of each channel and of the entire signal[16], the coefficient of variation for force steadiness[39], and the centroid of the EMG signal in the cranial-caudal and the medial-lateral directions[16]. This will be repeated for each contraction.

Intramuscular EMG analysis

A 27g monopolar electromyography needle will be placed into the midbelly of the upper fibers of the trapezius muscle using ultrasound guidance. The intramuscular EMG signals will be measured using Cadwell Sierra Wave. Since this system does not offer motor unit decomposition, we will use the intramuscular EMG analysis to provide us with more details of the gross EMG measurements such as the overall RMS value, the coefficient of variation for force steadiness, and the centroid measurements.

Determination of Central Sensitization:

Before measuring outcomes, approximately 20 minutes after capsaicin application we will analyze the area of secondary hyperalgesia for each study subject, then determine whether central sensitization has in fact been induced. The presence of central sensitization is confirmed by expansion of the receptive field and area of secondary hyperalgesia beyond the 25 cm² initial application area. If it has, the study participant will undergo the rest of the experimental methodology. If it has not, the capsaicin will be applied once more and the region of secondary hyperalgesia will be remeasured in 20 minutes later. The above described process for confirming the presence of central sensitization will take place again. If the study participant has not had sensitization at this stage they will be withdrawn from the study.

Primary Outcomes

The primary outcome measures:

1. Textural regional changes
2. Recruitment and Amplitude regional changes

These will be recorded for each arm of the study, please see figure 1.

Secondary outcomes:

1. A record of adverse events

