texture features will be computed in MATLAB and principal component analysis will be computed to reduce the variables. A repeated measures MANOVA will be applied for each intervention group. To test the change in EMG within and between groups a repeated measurement ANOVA will be applied considering each intervention group as a factor. The dependent variable would be considered as pain intensity, duration, and area of pain in separate analysis. Data distributions would be first checked with the Shapiro-Wilk to conform the normal distribution of the data. Additionally, we will test for the homogeneity of variance using Mauchly's test as well as correcting the degrees of freedom if necessary [40]. If the assumption of normality not met, for all skewed data an appropriate transformation will be used. We will construct univariate and multivariable linear regression models of differences in EMG amplitude (differences between after and before) as a function of intervention groups when adjusted for important covariates. Due to small sample size in each group, there is not possible to adjust for several covariates. Therefore, in a univariate model we will find the most important ones. For initial selection of relevant variables, all variables with a p-value ≤ 0.2 in the univariate analysis will be selected and retained in the multivariable analysis.

All Statistical analyses will be conducted with SAS for Windows (version 9.3; SAS Institute, Inc, Cary, NC). Using a two-sided test a P-value ≤ 0.05 will be considered as statistically significant.

Discussion

This will be the first study that assesses the effect of capsaicin induced central sensitization on ultrasound texture features and muscle motor unit activity. Findings from this

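### The p ≤ 0.2 covariate screen for the EMG amplitude regression is not limited to pre-allocation variables, so it can admit hyperalgesia area and remove the part of the effect that runs through sensitization

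*Combined protocol and SAP*

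**What the plan says.** The combined protocol and SAP, under Statistical analysis plan, fits linear regressions of the after-minus-before difference in EMG amplitude "as a function of intervention groups when adjusted for important covariates". Amplitude change is listed under Primary Outcomes.

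The choice of covariates is left to the data. The section first concedes a limit: "Due to small sample size in each group, there is not possible to adjust for several covariates". It then gives the remedy: "Therefore, in a univariate model we will find the most important ones". The operative rule is that "all variables with a p-value ≤ 0.2 in the univariate analysis will be selected and retained in the multivariable analysis". No candidate covariates are named anywhere, and no sentence limits them to values known before allocation.

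Two other sections create variables after allocation and before the outcome:

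- Under Inducing central sensitization: "The size of the region of secondary hyperalgesia will be measured to characterize the extent of central sensitization".
- Under Determination of Central Sensitization: "Before measuring outcomes, approximately 20 minutes after capsaicin application we will analyze the area of secondary hyperalgesia for each study subject". If sensitization is not shown, a second step follows: "If it has not, the capsaicin will be applied once more". A participant still not sensitized after that is withdrawn.

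The same statistical section also tests EMG change by repeated measures ANOVA with intervention group as a factor. It names pain intensity, duration and area as dependent variables of separate analyses.

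**The concern.** A covariate in a randomized comparison should not be something the treatment can change. The screen asks only whether a variable is associated with the outcome, and a variable on the causal path from capsaicin to EMG is associated with the outcome by construction. Hyperalgesia area is the plan's own measure of the mechanism that research question b proposes, and it is recorded for every participant before the outcome. Re-application is triggered by the same response.

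If area enters the model, the group coefficient no longer estimates the total effect of capsaicin. It estimates what is left once sensitization is held fixed. The more the hypothesis is true, the more likely area is to pass and the smaller the remaining coefficient.

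The rule also conflicts with the sentence that introduces it. Adjustment for several covariates is said to be impossible, yet every variable passing a loose threshold is kept. With ten irrelevant candidates, 10 × 0.2 = 2 would be retained on average.

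**Working it through.** The plan gives no figure on this point, so there is none to reproduce.

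**Inputs from the documents.** Screening threshold 0.2; two-sided alpha 0.05; recruitment target 84 (minimum 70). The sample size section counts seven groups and the design section describes six treatment groups, so both 7 × 12 and 6 × 14 were used; each gives 84.

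**Assumed, not in the documents.** The total effect, the shift capsaicin causes in area, and the share of the effect that runs through area.

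**Model.** Let A be hyperalgesia area and Y the EMG change:

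- A = a·dose + u
- Y = b·A + c·dose + e

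The total dose effect is T = ab + c and the mediated share is s = ab/T. A regression without A estimates T. A regression with A estimates c = (1 − s)T. With T = 0.75 SD this is 0.75 × 0.75 = 0.56 at s = 25%, 0.5 × 0.75 = 0.375 at s = 50%, and 0 at s = 100%.

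**Simulation 1.** Two routes × three doses × 14 = 84, linear dose trend, T = 0.75 SD at the high dose versus control, a = 1 SD, no withdrawals, 4,000 trials per setting:

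| Share s | A passes screen | Estimate without A | Estimate after screen | Power without A | Power after screen |
|---|---|---|---|---|---|
| 25% | 90.5% | 0.750 | 0.563 | 0.796 | 0.506 |
| 50% | 99.9% | 0.742 | 0.370 | 0.783 | 0.282 |
| 100% | – | 0.75 (set) | about 0 | – | 0.046 |

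**Check by hand.** Code dose as 0, 0.5, 1. Its variance is 1/6, so the sum of squares is 84/6 = 14. Take the SD of Y within a dose as 1.

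- Without A: SE = 1/√14 = 0.267; 0.75/0.267 = 2.81; power ≈ Φ(2.81 − 1.96) = 0.80.
- With A: the squared correlation of dose and A is (1/6)/(1 + 1/6) = 1/7, which inflates the variance by 7/6.
- s = 50%: residual variance 1 − 0.375² = 0.859; SE = √(0.859 × (7/6)/14) = 0.268; 0.375/0.268 = 1.40; power ≈ Φ(−0.56) = 0.29.
- s = 25%: residual variance 1 − 0.1875² = 0.965; SE = √(0.965/12) = 0.284; 0.5625/0.284 = 1.98; power ≈ Φ(0.02) = 0.51.

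These agree with the table. If the SD of 1 refers instead to the residual after A, simulation at s = 50% gives 0.76 to 0.38 SD and power 74% to 26%.

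**Simulation 2.** Seven groups of 12, two of them controls; group as a factor; T = 1.25 SD; a = 1 or 2 SD; 2,000 trials per setting. Ranges cover the two values of a:

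| Share s | A passes screen | Estimate without A | Estimate after screen | Power without A | Power after screen |
|---|---|---|---|---|---|
| 0% | 65–95% | 1.24–1.25 | 1.21–1.22 | 0.95–0.96 | 0.72–0.92 |
| 25% | 99.7% | 1.25–1.27 | 0.94–0.96 | 0.92–0.95 | 0.48–0.64 |
| 50% | 100% | 1.25–1.28 | 0.62–0.64 | 0.85–0.92 | 0.19–0.32 |
| 100% | 100% | about 1.25 | about 0 | 0.53–0.84 | 0.05 |

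Even with nothing mediated, area often passes because dose moves both area and outcome. The estimate is then nearly unchanged, but power falls.

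**Withdrawal rule.** Withdrawing unsensitized participants narrows the range of area. It is unclear whether the rule reaches the control arms, so both readings were tried, with T = 0.75 SD, s = 50% and an assumed cut-off 0.5 SD above the control mean:

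- All arms: area passes in 65% of trials; estimate 0.52 to 0.39 SD, a fall of 0.13/0.52 = 25%; power 23% to 15%.
- Capsaicin arms only: area passes in over 99%; estimate 0.96 to 0.39 SD, a fall of 0.57/0.96 = 59%; power 86% to 17%.

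A cut-off of 1.0 SD on all arms gives selection of 46%, estimate 0.49 to 0.40 SD, and power 14% to 11%.

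**The case against.** The strongest reply is that the model criticised is nowhere described. No section names hyperalgesia area, re-application or pain as a covariate, and the screen is called an initial selection. A reader might infer that these variables will be adjusted for. The documents do not support that: they leave the candidates open. What stands is that the rule, as written, lets them in.

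A reader might add pain to the list. The plan makes pain a dependent variable of separate analyses, so it is a poor example and the point does not rest on it.

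A reader might also infer that a null adjusted result would be taken to mean no capsaicin effect. Nothing makes the adjusted regression decisive. The repeated measures ANOVA does not use the screen, and with two time points its group-by-time test is the unadjusted comparison of change scores. The univariate regression would also be available, and the texture outcome is untouched. This limits the consequence, but the plan does not say which EMG analysis governs if they disagree.

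Finally, selection above 99% and power falling from 78% to 28% might be read as forecasts for this trial. They are not: they assume no withdrawals and an arbitrary mediated share. Under the all-arms reading of the withdrawal rule the loss attributable to the screen is much smaller, because much of the power has already gone through withdrawal, which is a separate matter. Attenuation remains under every reading tried.

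**Conclusion.** The point holds as a defect in one analysis of a primary outcome. The screen is not restricted to pre-allocation variables, it admits the plan's own marker of the hypothesised mechanism, and it contradicts the stated limit on the number of covariates. If area enters, the adjusted group coefficient loses a fraction equal to the mediated share: about a quarter, a half or all of it at 25%, 50% or 100% in the setting without withdrawals. The total effect, the shift in area and the mediated share are all assumed, so these figures are illustrations. The direction of the loss follows from the model if area lies on the path from capsaicin to EMG change. The change is worth making, but the between-group EMG conclusion does not depend on this regression alone.

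**What to change.** Delete the p ≤ 0.2 screen and replace it with text along these lines: *The adjusted model for EMG amplitude change will include intervention group and the following covariates recorded before allocation: [short list, for example baseline EMG amplitude and sex]. Area of secondary hyperalgesia, re-application of capsaicin and any other variable measured after allocation will not be covariates in the group comparison.* If the relation of those variables to EMG change is of interest, report it as a separate analysis labelled exploratory.

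The cost is one or two sentences and no new data. What is given up is the data-driven choice of covariates. A short fixed list also removes the conflict with the plan's statement that only a few covariates can be supported.
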